## **31. PROCESS TO DOCUMENT CONSENT IN WRITING**

Written informed consent will be given to participants who are patients (not caregivers or providers, who will receive a Fact Sheet). All study staff members who a part of this study will be trained properly and have a complete understanding of all study related documentation in order to help answer any questions participants may have. The approaching staff member will assess the capacity of the patients to consent; we have submitted to the IRB a "Capacity for Informed Consent" form that can be used. We anticipate that due to the study selection criteria (older patients), some patients will not be able to provide informed consent. Thus, all patients will be assessed for their understanding of the study, the risks and benefits associated with the study, the voluntary nature of participation, and the confidential nature of all study data. If patients answer 3 or more questions out of 8 incorrectly, they will be deemed unable to provide informed consent and excluded. Safeguards will be put into place to protect the rights of cognitively impaired participants.

For caregivers and providers, we will obtain informed consent via an unsigned fact sheet given to them prior to study visits.

All participants who sign the consent form will be given a copy to keep for their own records. The study team will keep the original copy of the signed consent forms in a locked cabinet in a locked room. The study team will also make another copy and send it to UMMMC Medical records to be kept on file for each patient who participates in the research.

Please see Section #30: Consent Process for information regarding consenting patients during COVID-19 restrictions.

To minimize patient burden during this time, we are requesting a waiver of documentation of written consent for subjects. We attest that all of the following are true:

- The research involves no more than minimal risk to the subjects.
- The research involves no procedures for which written consent is normally required outside of the research context, and all study activities are conducted over the telephone or Zoom.

• Subjects will be provided a written statement including the elements of consent (described on the COVID Informed Consent Form).

### **32. DRUGS OR DEVICES**

This study will use only commercially available devices (Samsung gear, Android smartphones) or FDA approved devices (AliveCor Kardia Mobile device and app). Part II participants will use the AliveCor Kardia Mobile devices and smartphones that will only run the AliveCor app (FDA approved for single-lead ECG recording) and the Pulsewatch app. A gold-standard, commercially available (Cardiac Insight Cardea Solo) monitoring technology will be deployed and used by all Part II participants. We have enclosed a copy of the FDA approval letter for both AliveCor and Cardiac Insight into this submission. In addition, we have also enclosed a copy of detailed information regarding these devices for any review.

The mobile device application (Pulsewatch App) that will be developed in this study at the end of Part I is not commercially available nor FDA approved. This application (Abbreviated IDE) is only to be used with participants of this study. For this reason, we would like to document the following:

i. The device is not a banned device;

ii. The device is not intended as an implant that presents a potential for serious risk to the health, safety, or welfare of a subject;

iii. The device is not purported or represented to be for a use in supporting or sustaining human life that presents a potential for serious risk to the health, safety, or welfare of a subject;

iv. The device is not for a use of substantial importance in diagnosing, curing, mitigating, or treating disease, or otherwise preventing impairment of human health that presents a potential for serious risk to the health, safety, or welfare of a subject: and

v. The device does not otherwise present a potential for serious risk to the health, safety, or welfare of a subject.

vi. The device will be labeled in accordance with 21 CFR 812.5.

vii. The PI as sponsor will

1. Comply with the requirements of 21 CFR 812.46 with respect to monitoring investigations

2. Maintain the records required under 21 CFR 812.140(b) (4) and (5) and make the reports required under 21 CFR 812.150(b) (1) through (3) and (5) through (10)

3. Ensure that participating investigators maintain the records required by 21 CFR 812.140(a)(3)(i) and make the reports required under 21 CFR 812.150(a) (1), (2), (5), and (7)

4. Comply with the prohibitions in 21 CFR 812.7 against promotion and other practices

Statistical Plan

Smartwatch Monitoring for Atrial Fibrillation After Stroke

NCT #: NCT03761394

Date of document: 11/20/18

Pulsewatch Statistical Plan:

Pulsewatch usability assessment via qualitative interviews and focus groups: Interviews will seek individual opinions about the usability and acceptability of Pulsewatch and will ask about: 1) ways in which Pulsewatch was intrusive; 2) how using Pulsewatch caused fatigue; 3) ways in which participants thought Pulsewatch use promoted health; 4) reflections on the trustworthiness of Pulsewatch (e.g., ‘belief’ of findings); and 5) participant comfort using Pulsewatch to communicate with their clinician. We anticipate that these 5 areas are highly individual and vary from person-to-person. Therefore, qualitative interviews, rather than standardized questionnaires, are needed since they provide an opportunity for users to describe their personal experiences in detail. In addition, we will ask participants to identify the amount of time they spent using Pulsewatch during a typical day. To assess another measure of participant’s acceptance, we will ask the participant to gauge their interest in continuing to use Pulsewatch even though their participation in the study has concluded. Participants who ceased using Pulsewatch will be identified and contacted by the staff for semi-structured interviews to understand why they stopped. We will conduct 2-4 focus groups (12-16 users total) to generate data on barriers to, and facilitators of, Pulsewatch use. In distinction to Aim 1 focus groups, which focus on learning what capabilities users want, Aim 3 focus groups center on ‘what worked’ and ‘what didn’t’ and whether or not long-term use introduces or reduces stress. We will also solicit feedback on the Interactivity Manager and Annotation Panels, features developed too late in Aim 1 to be fully explored by Aim 1 focus groups. Groups will be stratified by Pulsewatch adherence during the intervention period (<50%, 50-74%, >75%). We anticipate that with 4 focus groups we will reach saturation. However, if this is not the case, we will conduct 2 additional groups (n=12). Semi-structured and open-ended agendas will be written and IRB submitted. Discussions will be audio-recorded, transcribed and de-identified, protecting confidentiality by replacing names with study IDs.

Data Analysis: Sample Size and Adequacy of the Proposed Population. For Aim 1, we will recruit 30-40 stroke/TIA patients and 5-10 providers to participate in focus groups and interviews. 4 UMass Memorial Medical Center (UMMC) cardiologist/neurologists see 500 outpatients yearly with stroke/TIA in the UMMC neurology/cardiology clinic, requiring a recruitment rate of 3% over 6 months. We will recruit 120 participants with cryptogenic stroke admitted to the UMMC Stroke Service over a 33-month period. Since the UMMC Stroke Service discharges 143 patients with cryptogenic stroke yearly, we require a recruitment rate of 31% over 33 months.

Qualitative data analysis (Aims 1 and 3): Table 1 summarizes the planned qualitative analyses and outcomes.

Research need	Aim	Method	Participants	Analysis	Outcome	Timing
Formative patient & provider input into Pulsewatch design & development	1	4-6 focus groups; 6-8 participants (ppts) each	30-40 app naive ppts; 6-10 stroke medical providers will use a fully realized demo app and provide feedback on interfaces and usability	coding & thematic analysis	Feedback on prototype. Barriers & facilitators of use. Preferences & usability of features. Enhancements to text and ambient messaging. Provider information. Communication system design.	Before app refined
Communication among development team	1	Hack-a-thon	Patients, medical providers, behavioral scientists, computer programmers	coding & thematic analysis	Ensures developers hear patient and provider needs. Feedback on information display, graphical images, & message content.	App actively refined
Post-deployment eval of Pulsewatch	3	2-4 focus groups; 6-8 ppts each	12-16 ppts	coding & thematic analysis	Feedback on information display, graphical images & message content.	After app use
Post-deployment eval of Pulsewatch	3	20 min qualitative interviews	30 stroke survivors who use PULSEWATCH for 1 month	framework analysis	Impact of app use on quality of life, anxiety, & selfactivation	After app use

Qualitative analyses will involve a multi-step process, using applied thematic content analysis of all focus groups. In thematic analysis, all relevant qualitative data is assigned to specific codes (e.g., interface). The codes are then read in aggregate to identify key themes (e.g., large fonts needed). The Principle Investigator and co-investigator will develop transcript codes. The focus groups conducted in Aim 1 will be analyzed in Year 1 and will inform the Hack-a-thon; those conducted in Aim 3 will be analyzed separately in Year 4. Deductive codes will be drawn from the topics in the questions used to facilitate the focus groups and interviews. This coding scheme will be developed during close review of the transcripts, which also allows the creation of inductive codes to capture any themes that emerge from the discussions themselves. Two

coders will independently code each transcript. Coded transcripts will then be compared to ensure comprehensiveness and to reconcile discrepant results. Agreed upon codes will be entered into NVivo 10 (Version 10, QSR International, Australia) for analysis. NVivo 10 allows sorting of data based on relevant demographic variables. Thus, our thematic analysis will investigate whether there are differences in content related to sex or whether pAF was diagnosed. A framework analysis will be conducted on the 30 semi-structured summative interviews with Pulsewatch users (Aim 3). This qualitative data reduction technique is used with large data sets to review, summarize and classify data; it is particularly appropriate for practice-oriented findings and it is often used in health-related research.¹¹³ NVivo 10 includes a framework analysis tool and will be used to manage data and facilitate the analyses.

Quantitative data analysis (Aims 2 and 3): Table 2 summarizes the primary quantitative analyses and outcomes. **As for Aim 1, for all Aim 2 and 3 analyses, we will examine the effect of sex (a biological variable) on study outcomes.**

Research goals	Aim	Participants	Outcomes	Covariates/predictors	Statistical Methods
Evaluate Pulsewatch performance against gold standard	2	90 Pulsewatch users	pAF determined by 14-day cardiac event monitoring	Number and percentage of AF readings over 14 days	Logistic regression to produce area under the ROC curve (AUC)
Determine effects of patient characteristics on Pulsewatch performance	2	90 Pulsewatch users	Area under the curve	Patient characteristics (e.g., sex, hearing or visual impairment)	Chi-square test to compare AUC of 2 independent ROC curves
Examine Pulsewatch usability	3	30 Pulsewatch users	Indicator of watch daily use (yes vs. no) over 1 month	Sex, cognitive function, social support, depression, Barthel)	Mixed effects logistic regression model
Evaluate the impact of Pulsewatch use on key patient-reported outcomes	3	30 Pulsewatch users and 30 controls	Stroke-related quality of life, anxiety & self-activation (Δ from baseline -1 mo)	Potential confounders (e.g. sex, medication adherence and disease-management self-efficacy)	t-test and linear regression model

Aim 2 Analysis: The analysis will focus on examining the performance of Pulsewatch worn for 9 hours daily for 14 days compared to 14-day cardiac monitoring, CardioKey by Biotel. A participant will be classified as having or not having pAF at the end of 14 days based on the gold standard. The total number of positive readings collected over 14 days from Pulsewatch (min 1 pulse every 5 minutes for 504 samples) will be used as the independent variable in a logistic regression to predict the binary outcome of pAF (yes vs. no). The area under the receiver operating characteristic (ROC) curve (AUC) will be calculated based on the results from the logistic regression to evaluate Pulsewatch performance for pAF screening. From the ROC curve, we can identify the cutoff point of total number of positive readings that produces the highest sensitivity and specificity combination. Similar analysis will be conducted using the % of positive readings among all readings collected from each participant as the independent variable. The 95% confidence intervals (CI) of the AUC will be calculated using formula given by Hanley and McNeil. We will then conduct exploratory analyses to examine whether characteristics affect watch performance over 14 days. For example, we will compare the area under 2 independent ROC curves of female vs. male participants (or vision impaired vs. not) using a chi-square test.

Aim 2 Power: Preliminary data suggest that Pulsewatch will have sensitivity, specificity and AUC of at least .9 to detect pAF. We calculate the width of 95% CI for AUC that ranges from .90 to .95 using the proposed sample size of 90 and an estimated rate of 20% patients with pAF. The width of the 95% CI ranges from .14 to .20. The proposed sample size will therefore give a quite precise estimate of Pulsewatch performance relative to the gold standard.

Aim 3 Analysis: The primary analysis focuses on app adherence use in 30 users asked to continue to use the watch and upload readings daily for 1 month. We will determine daily adherence (yes vs. no) based on whether or not daily smartwatch pulse recordings are present. We will examine whether participant characteristics, e.g., sex, cognitive impairment, or a high degree of stroke-related disability (Barthel Index), affect the likelihood of adherence over the 1 month study period. We will use a mixed effects logistic regression model including the participant as the random effect to capture the correlation among repeated measures from the same participant, uses participant characteristics as the fixed effects, and a binary indicator of daily adherence as the dependent variable. We will also examine the adherence time-trend by

including time (day) as a fixed effect in the model and patient as a random effect to estimate the slope of adherence over time. To examine whether the time trend varies by participant characteristics, we will include the interaction between characteristics and time in the model so that the slope of adherence over time can be estimated for each category of patient characteristic variables and be compared among the categories (e.g., pAF diagnosed vs. no pAF). Secondary analyses will examine rates of adherence to Pulsewatch ECG prompts and will compare Pulsewatch users to the usual care group with respect to stroke-related quality of life, anxiety, and self-activation. We will calculate the change score between baseline and 1 month as dependent variable. First, a *t*-test will be used to compare 2 study groups on the change score. A linear regression model, which will include group indicator (Pulsewatch users vs. usual care) as the independent variable and possible confounders (e.g., medication adherence and patient demographics) as covariates, to estimate adjusted group differences on the change scores.

Aim 3 Power: For the primary analysis, a power analysis was conducted comparing the time-averaged probability of adherence between 2 groups using a repeated measures regression model. We used 12 and 18 patients (total=30) in each of the groups (e.g., cognitively impaired vs. not), and type I error=5%. With 30 adherence measures for each patient and the probability of adherence in 1 group (e.g., cognitively impaired) = 50%, we will have 80% power to detect a difference in the adherence of 12%-16% in the other group when auto-correlation ranges from .2-.5). The difference in the probability of adherence decreases to 9%-12% when the probability in 1 group=80%. Therefore, our proposed n=30 for Pulsewatch users provides sufficient power to detect differences in the probability of adherence of 9%-16% between 2 groups (e.g., cognitively impaired vs. not). The secondary analysis power calculation was conducted comparing 30 users to 30 controls on continuous outcomes (e.g., anxiety) using a *t*-test. We will have a power of 80% to detect an effect size of .74 with 5% type I error.

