## 4) **Objectives\***

The objectives of this project are to develop a mobile device application with providers and patients that is both usable and accurate. The mobile device application will collect and extract RR interval data and use real-time algorithms for accurate detection of atrial fibrillation (AF) from mobile devices, including a smartwatch. Our central hypothesis is that a wrist-based wearable paired with a smartphone application will detect paroxysmal AF (pAF) with high sensitivity and specificity when compared to conventional cardiac monitors and will be found acceptable by stroke and cardiology patients and their providers. To accomplish this goal, our study will have two phases, a developmental phase and a testing phase. The overall objective will be accomplished by testing our central hypothesis after achieving the following specific aims:

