To fine tune and maximize the accuracy of our MNA algorithm, we will use data collected on AF subjects (Aims 2 and 3) using the Pulsewatch system. We will compare the performance of our MNA algorithm using the Pulsewatch signal to the simultaneous gold-standard Cardiac Insight patch. The data analysis and statistical evaluations will be similar to our recently published article on our MNA detection/reconstruction algorithm, but will also involve calculation of absolute error of the estimated heart rate via our algorithm to the reference Holter ECG-derived heart rate. Moreover, we will calculate sensitivity, specificity and accuracy of AF detection using our algorithm when compared to Cardiac Insight patch data.

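### The SAP's precision claim for 90 users is supported for the AUC only; sensitivity rests on about 18 AF cases, is less precise, and has no planned interval or correction for a cutoff chosen on the same data

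*SAP*

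**What the plan says.** The protocol's central hypothesis (section 4, Objectives) is that the device "will detect paroxysmal AF (pAF) with high sensitivity and specificity when compared to conventional cardiac monitors". It does not mention the AUC.

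The SAP's Aim 2 Power paragraph begins: "Preliminary data suggest that Pulsewatch will have sensitivity, specificity and AUC of at least .9 to detect pAF". It then calculates precision for the AUC alone, for AUC values of .90 to .95, "using the proposed sample size of 90 and an estimated rate of 20% patients with pAF". It reports a 95% CI width of .14 to .20 and ends: "The proposed sample size will therefore give a quite precise estimate of Pulsewatch performance relative to the gold standard".

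The SAP's Aim 2 Analysis paragraph says how sensitivity and specificity would arise: "From the ROC curve, we can identify the cutoff point of total number of positive readings that produces the highest sensitivity and specificity combination". The only interval it plans is for the AUC: "The 95% confidence intervals (CI) of the AUC will be calculated using formula given by Hanley and McNeil". The protocol repeats both statements in section 13, AF Detection Analysis. Neither place plans an interval for sensitivity or specificity, or any allowance for choosing the cutoff on the data used to measure accuracy.

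**The concern.** Sensitivity is estimated from participants with pAF only, whereas the AUC draws on every case and non-case pair. A sample can therefore support an adequate AUC interval and still say much less about sensitivity. The SAP carries its conclusion from the AUC to device performance in general, in a paragraph that has just named sensitivity and specificity as expected results.

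A second problem compounds this. A cutoff picked because it gives the best sensitivity and specificity in 90 people will look better in those 90 than in new patients. If a sensitivity near .9 were reported at that cutoff with no interval and no correction, readers would see neither its uncertainty nor its upward bias. For a screening tool, sensitivity is the measure that counts missed AF.

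**Working it through.** **Inputs.** From SAP Aim 2 Power: n = 90, pAF rate 20%, AUC .90 to .95, sensitivity and specificity at least .9. The SAP does not print the case counts. They follow as 90 × .20 = 18 cases and 90 − 18 = 72 non-cases.

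**Step 1: reproduce the SAP's figure.** The Hanley-McNeil standard error is

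SE = √{[A(1−A) + (n₁−1)(Q₁−A²) + (n₀−1)(Q₂−A²)] / (n₁n₀)}, with Q₁ = A/(2−A), Q₂ = 2A²/(1+A), n₁ = 18, n₀ = 72.

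- A = .90: [.0900 + 17(.8182 − .8100) + 71(.8526 − .8100)] / 1296 = 3.256/1296, so SE = .0501 and width = 2 × 1.96 × .0501 = .196.
- A = .95: [.0475 + 17(.9048 − .9025) + 71(.9256 − .9025)] / 1296 = 1.729/1296, so SE = .0365 and width = .143.

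These match the SAP's .20 and .14.

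**Step 2: sensitivity and specificity at the same inputs.** The exact (Clopper-Pearson) limits are the .025 quantile of Beta(x, n−x+1) and the .975 quantile of Beta(x+1, n−x).

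| Measure | Count | Estimate | Exact 95% CI | Width | Wilson 95% CI |
|---|---|---|---|---|---|
| Sensitivity | 17/18 | .944 | .727 to .999 | .27 | .74 to .99 |
| Sensitivity | 16/18 | .889 | .653 to .986 | .33 | .67 to .97 |
| Specificity | 65/72 | .903 | .810 to .960 | .15 | .81 to .95 |

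With 18 cases, 17/18 is the smallest count that meets the SAP's expectation of at least .9. The count 16/18 is nearest to .9 but falls just below it.

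**Step 3: like-for-like comparison.** The Hanley-McNeil width is a normal approximation, so the fair comparator is the Wald width. At sensitivity .90 with 18 cases this is 2 × 1.96 × √(.90 × .10/18) = .277. The ratio to the widest AUC interval is .277/.196 = 1.4.

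**Step 4: effect of choosing the cutoff on the same data.** Data were simulated with 18 cases and 72 non-cases, 6,000 runs per setting. The cutoff maximised sensitivity plus specificity. Both that rule and the score distributions are assumptions, since the SAP specifies neither.

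| Score distribution | Apparent sensitivity | True sensitivity at that cutoff | Gap |
|---|---|---|---|
| Binormal, AUC .90 | .871 | .793 | .078 |
| Binormal, AUC .95 | .921 | .856 | .065 |
| Zero-inflated counts, AUC .929 | .861 | .813 | .048 |
| Zero-inflated counts, AUC .950 | .890 | .840 | .050 |
| Zero-inflated counts, AUC .875 | .791 | .727 | .064 |
| Zero-inflated counts, AUC .910 | .831 | .794 | .037 |

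The gap for sensitivity is thus about .04 to .08. For specificity in the binormal settings it is smaller: .833 against .815, and .890 against .875.

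**Step 5: would the proposed remedies work?** Across the six settings the exact interval at the chosen cutoff covered the true sensitivity in .958 to .980 of runs, so a simple interval is adequate. A bootstrap optimism correction (600 runs, 200 resamples, binormal) gave apparent, corrected and true values of .867, .820 and .791 at AUC .90. It removed (.867 − .820)/(.867 − .791) = .047/.076, or about 60% of the bias. At AUC .95 the values were .921, .882 and .852, a removal of .039/.069, or somewhat under 60%.

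**The case against.** The strongest reply is that SAP Table 2 and the Aim 2 Analysis paragraph measure performance by the AUC, so the precision claim means the AUC and is correct. That stands as far as it goes: no printed figure is wrong. It does not close the gap, because the hypothesis names sensitivity and specificity and the Aim 2 Power paragraph opens by expecting values for both.

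It is also fair to say that the SAP states only that a cutoff can be identified. It does not commit to reporting sensitivity at that cutoff as the study's accuracy result, so an uncorrected estimate without an interval is something the plan permits, not something it announces. In addition, the precision claim appears in the SAP only. The matching sentence in the protocol's AF Detection Analysis is broken off in the available text and cannot be judged.

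The bootstrap is less essential than the interval, since the exact interval already had adequate coverage. It is still worth giving, because an interval does not move an optimistic point estimate.

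A reader might infer several stronger things that the documents do not support:

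- **That the plan's own inputs imply a sensitivity interval reaching down to .65.** That limit belongs to 16/18, which is below the expected .9. At 17/18 the lower limit is .73.
- **That sensitivity is 1.7 times as imprecise as the AUC.** This sets an exact width (.33) against a normal-approximation width (.20). The like-for-like figure is 1.4.
- **That the simulation shows how rarely the device would truly reach .9.** Under equal-variance binormal scores, the best equal sensitivity and specificity is .82 at AUC .90 and .88 at AUC .95. Both reach .9 only at an AUC of about .965. The simulated settings therefore exclude the SAP's premise, and only the optimism gap can be taken from them.
- **That the protocol's separate accuracy calculation shares the defect.** Section 13, Smartwatch Data, says "we will calculate sensitivity, specificity and accuracy of AF detection using our algorithm when compared to Cardiac Insight patch data" but gives no unit of analysis. If it is per segment, the 18-case arithmetic does not apply.

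**Conclusion.** The point holds in a limited form. The SAP's statement about precision is justified for the AUC and not for sensitivity. With 18 cases, a sensitivity meeting the SAP's expectation would carry an exact 95% CI of about .73 to 1.00, and one just below it .65 to .99. Specificity is not the problem: at about .15, its exact width lies at the low end of the AUC range. Any sensitivity read at the data-chosen cutoff is biased upward, by about .04 to .08 under the assumed distributions.

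The intervals rest on the SAP's 20% pAF rate, which is accepted here. They would change with the case count: as assumed alternatives, 8/9 gives .52 to 1.00 and 24/27 gives .71 to .98. They do not depend on any score distribution; the size of the optimism does.

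Nothing here invalidates the AUC analysis or shows that 90 users are too few for it. This is a cheap improvement in what is stated and reported.

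**What to change.** 1. In the SAP's Aim 2 Analysis and the protocol's AF Detection Analysis, add exact or Wilson 95% CIs for sensitivity and specificity at the chosen cutoff. State the rule that picks the cutoff. Beside each apparent value, give a bootstrap optimism-corrected one that repeats the cutoff choice in every resample, and note that the correction removes only part of the bias.
2. In the SAP's Aim 2 Power paragraph, limit the precision claim to the AUC. Add the intervals expected with 18 cases and 72 non-cases: sensitivity .73 to 1.00 for 17/18 and .65 to .99 for 16/18, and specificity .81 to .96 for 65/72.

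The cost is a few sentences and one further analysis of data already being collected. Sample size, enrolment, monitoring and the interim rule on AF rate do not change. The one drawback for the sponsor is that reported sensitivity will be slightly lower and visibly less certain.

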## Part II (Aims 2-3):

-To evaluate the performance of a smartwatch for pAF detection in stroke patients and/or to monitor patient who are at stroke risk with  $CHA_2DS_2$ -VASc score  $\geq 3$  by examining over 14 days the accuracy of pAF detection from Pulsewatch vs. a state-of-the-art cardiac monitoring device.

-To evaluate rates of adherence and factors associated with successful longer-term smartwatch use among up to 60 randomly selected stroke patients and/or who have a  $CHA_2DS_2$ -VASc score  $\geq$ 3 enrolled in our 14-day validation study. These randomly selected participants will be asked to use the smartwatch/phone dyad for 30 days. We will explore the impact of smartwatch use over 30 days on patient-reported quality of life, anxiety, and self-efficacy compared up to 60 usual-care patients.

Learnings from these new objectives will support our future goal to extend monitoring periods to many months or years, surpassing the capabilities of event monitors.

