## Adherence Analysis:

In Aim 3 of Part II of the study, adherence will be operationalized to determine whether pulse recordings were present on each day over the 30-day period. We will examine whether participant characteristics, e.g., sex, cognitive impairment, or stroke-related quality of life, affect the likelihood of adherence over the 1-month study period. We will use a mixed effects logistic regression model, including the participant as the random effect to capture the correlation among repeated measures from the same participant, using participant characteristics as the fixed effects, and a binary indicator of daily adherence as the dependent variable. We will also examine the adherence time-trend by including time (day) as a fixed effect in the model and participant as a random effect to estimate the slope of adherence over time. To examine whether the time trend varies by participant characteristics, we will include the interaction between characteristics and time in the model so that the slope of adherence over time can be estimated for each category of participant characteristic variables and be compared among the categories (e.g., pAF diagnosed vs. no pAF). Secondary analyses will examine rates of adherence to Pulsewatch ECG prompts and will compare Pulsewatch users to the usual care group with respect to stroke-related quality of life, anxiety, and self-activation. We will calculate the change score between baseline and 1 month as a dependent variable. First, a t-test will be used to compare 2 study groups on the change score. We will use a linear regression model, which will include group indicator (Pulsewatch users vs. usual care) as the independent variable and possible confounders (e.g., medication adherence and participant demographics) as covariates, to estimate adjusted group differences on the change scores.

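### The SAP's Aim 3 power figures are for 30 users and 30 controls, while the protocol plans up to 60 of each, and they name no correlation structure that can be matched to the planned participant random-effect model

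*SAP*

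**What the plan says.** The SAP, under Aim 3 Power, bases the primary calculation on "comparing the time-averaged probability of adherence between 2 groups using a repeated measures regression model", with 12 and 18 users, 30 daily measures each and a 5% type I error. With 50% adherence in one group it states "we will have 80% power to detect a difference in the adherence of 12%-16% in the other group when auto-correlation ranges from .2-.5"; with 80% in one group the difference is 9%-12%. It concludes: "Therefore, our proposed n=30 for Pulsewatch users provides sufficient power to detect differences in the probability of adherence of 9%-16% between 2 groups". For the secondary t-test on 30 users and 30 controls it states: "We will have a power of 80% to detect an effect size of .74 with 5% type I error". SAP Table 2 repeats the size for patient-reported outcomes as "30 Pulsewatch users and 30 controls".

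The planned adherence model, in the SAP under Aim 3 Analysis, is a "mixed effects logistic regression model including the participant as the random effect to capture the correlation among repeated measures from the same participant". The protocol, section 13 (Adherence Analysis), has the same: a "mixed effects logistic regression model, including the participant as the random effect". It gives no power figure.

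The protocol's sizes are larger. Section 4 (Part II) refers to "successful longer-term smartwatch use among up to 60 randomly selected stroke patients", with up to 60 usual-care patients for comparison. Section 24 also says up to 60 users. Section 11 and section 25 give 60 in each Aim 3 arm without that qualifier. The SAP is dated 11/20/18; the protocol text (V 1.5) contains COVID-19 procedures and so is later.

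**The concern.** The SAP paragraph is the only power statement for Aim 3, and it differs from the plan in two respects. Its numbers of users and controls are half the protocol's. It also quotes a correlation of .2-.5 without saying how that correlation behaves across 30 days, and this matters a great deal. If the correlation fades with each day apart, 30 daily readings carry much independent information. If each person has a stable tendency to wear or not wear the watch, as a random intercept assumes, they carry far less.

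The sentence that 30 users are enough carries no such condition. At stake is how a null result for, say, cognitive impairment or sex would be read: it could be taken as evidence of no difference when the study's ability to see one had not been established under the model used.

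**Working it through.** **Inputs.** From the SAP: 12 and 18 users, 30 days, type I error 5%, 80% power, reference adherence 50% or 80%, correlation .2-.5, and 30 vs 30 for the t-test. From the protocol: up to 60 and 60. Assumed, because the documents do not say: two-sided testing; a 24/36 split of 60 users (the SAP's 2:3 ratio); 50 per arm as an illustration of loss; the random effect read as a random intercept; and the value of any constant correlation.

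**Formula.** Unpooled normal approximation, with correlation measured between two days' yes/no adherence in one person:

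d = (1.96 + 0.842) × √{ (DE/30) × [p1(1−p1)/n1 + p2(1−p2)/n2] }

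- Decaying correlation, AR(1): DE = 1 + 2Σ(1 − k/30)r^k for k = 1 to 29. This is 1.48 at r = .2 and 2.87 at r = .5.
- Constant correlation: DE = 1 + 29ρ. This is 6.8 at .2 and 15.5 at .5.

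**Step 1: reproduce the SAP (12/18).**

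| Structure, .2 / .5 | From 50% | Increase from 80% |
|---|---|---|
| SAP states | 12 / 16 points | 9 / 12 points |
| Decaying | 11.5 / 15.8 | 8.6 / 11.5 |
| Constant | 23.7 / 33.9 | 16.5 / not attainable |

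The decaying structure gives all four stated figures after rounding. The 9%-12% fits an increase only: a decrease from 80% needs 9.8-13.9 points. Pooled variance, one-sided testing and swapping the groups did not bring the constant-correlation result from 50% below 20.9 points. The average between-day correlation under the decaying structure is (DE − 1)/29, that is .017 at r = .2 and .064 at r = .5. So an autocorrelation of .2-.5 stands for much weaker clustering than a constant .2-.5.

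**Step 2: the constant correlation that still gives 80% power.** Solve the formula for DE, then ρ = (DE − 1)/29. Example, 50% vs 62% with 12/18: the variance term before DE is (.25/12 + .2356/18)/30 = .001131; (.12/2.802)² = .001835; DE = 1.62; ρ = .62/29 = .021.

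| Split | 50 v 62 | 50 v 66 | 80 v 89 | 80 v 92 |
|---|---|---|---|---|
| 12/18 | .021 | .067 | .022 | .074 |
| 24/36 | .077 | .168 | .079 | .183 |

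**Step 3: size alone.** Keeping the SAP's decaying correlation and moving to 24/36, power at the stated differences is 98%-99%. For the t-test (noncentral t), the detectable effect size is .736 at 30 per arm, which reproduces .74; it is .57 at 50 per arm and .52 at 60 per arm.

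**Step 4: detectable differences at 60 users (24/36), constant correlation.**

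| ρ | DE | From 50% | Increase from 80% | Decrease from 80% |
|---|---|---|---|---|
| .05 | 2.45 | 10.5 points | 7.9 | 8.9 |
| .10 | 3.90 | 13.1 | 9.7 | 11.4 |
| .20 | 6.80 | 17.2 | 12.4 | 15.2 |
| .50 | 15.5 | 25.2 | 17.3 | 23.4 |

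The 17.3-point increase ends near 97%, where a normal approximation on this few people is unreliable.

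**The case against.** The strongest reply is that nothing is shown to be wrong with the trial. The SAP's arithmetic reproduces. The larger protocol size helps, and since parts of the protocol say up to 60, the figure is a ceiling that 30 does not exceed. Planning a mixed model with a marginal repeated-measures approximation is common practice. Neither document says random intercept or rules out residual serial correlation, and a random slope over days would not give a constant correlation either. All of this stands. It limits the point to an outdated size and an unstated structure.

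Two stronger readings are tempting. First, a reader might infer that Aim 3 is underpowered: inserting .2-.5 as a constant correlation gives power of 23%-28% with 30 users and 41%-50% with 60 at the SAP's paired differences. The documents do not support this. They call .2-.5 an autocorrelation, and they give no constant correlation. With 60 users and a constant correlation of .05, power at the stated differences (increases, for those from 80%) is 90%-99%.

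Second, a reader might infer that the SAP figures can come only from a decaying correlation. That structure is inferred from fit and only two structures were tried at .2-.5; a constant correlation of about .02-.07 also supports the stated differences.

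The reply does not remove the need to say which structure was meant, because the sufficiency sentence is unconditional and the larger size does not guarantee 80% under every structure.

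**Conclusion.** The point holds as a mismatch between documents and an unstated assumption. The size mismatch is plain from the text, works in the SAP's favour, and changes the secondary detectable effect size from .74 to about .52 at 60 per arm.

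The correlation part is conditional on reading the random effect as a random intercept. On that reading the 80% claim holds only if the constant within-person correlation is at most about .02-.07 with the SAP's 12/18 split, or about .08-.18 with 60 users split 24/36. Because the documents give no such correlation, whether there is a shortfall is unknown, and so is its size. The figures are approximations on the probability scale, while the planned test is on the log-odds scale; a simulation with constant correlation gave power a few points lower (for example 47% against 49% for 50 v 62 at .2 with 60 users). This should be fixed, but it does not invalidate the trial.

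**What to change.** Change the SAP's Aim 3 Power text as follows:

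- Restate both calculations at the protocol's size and bring Table 2 into line.
- Name the correlation structure, make it consistent with the random-effect model, and say whether that effect is an intercept only.
- Show a range of correlations. With 60 users (24/36 assumed) at constant .05, .10, .20 and .50, the detectable difference from 50% is about 10, 13, 17 and 25 points. From 80% it is about 8, 10, 12 and 17 for an increase (mark the last as unreliable) and 9, 11, 15 and 23 for a decrease. State the direction.
- Make the sentence that 30 users suffice conditional on the stated correlation, or remove it.
- Give the secondary effect size as about .52 at 60 per arm, or .57 if 50 per arm are analysed.

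The cost is wording only, with no extra participants. The downside is that the adherence statement becomes less favourable than the present one if the constant correlation exceeds about .08; the secondary statement improves.
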